4.3.2.2. Justification of Dose and Administration Sequence of Voruciclib + Venetoclax

In vitro studies indicate that voruciclib has the potential to inhibit CYP3A4 and P-gp (Section 4.15). At the proposed starting dose of voruciclib of 50 mg, an increase of venetoclax exposure may be observed based on the following assessment of time dependent inhibition of CYP3A4 by voruciclib.

CYP3A4 time-dependent inhibition potential of voruciclib

The CYP3A4 time-dependent inhibition potential of voruciclib was evaluated according to FDA guidance (In Vitro Drug Interaction Studies - Cytochrome P450 Enzyme- and Transporter-Mediated Drug Interactions) using the following input parameters.

Parameter	Value (source)
Voruciclib dose	50 mg
Voruciclib C _{max} after 50 mg multiple dose	225 ng/mL or 0.225 mg/L (extrapolated; IB Section 5.2.1.1)
Fraction unbound in plasma	0.05 (IB Section 4.3.2)
Fraction absorbed after oral administration	80% (preclinical data; IB Section 4.3.1)
Fraction available after intestinal metabolism	100% (unknown; assumed per FDA guidance)
K _a	0.67 h ⁻¹ (assumed based on slow absorption as evidenced by median T _{max} 4 to 6 hours; IB Section 5.2.1.1)
Blood: Plasma ratio of concentration	1 (unknown; assumed)
k _{inact}	0.021 min ⁻¹ (estimated from raw data; Study No. P1446APK16)
K _I	5.0478 mg/L (estimated from raw data; Study No. P1446APK16)
K _{deg,CYP3A4, liver}	0.00032 min ⁻¹ (literature)
K _{deg,CYP3A4, interstine}	0.00048 min ⁻¹ (literature)
Hepatic blood flow	97 L/h (according to FDA guidance)
Blood flow in enterocytes	18 L/h (according to FDA guidance)

Based on the input parameter values listed in the table above, the effect of voruciclib on the PK of midazolam (a sensitive CYP3A4 substrate) was assessed. For these calculations, midazolam $f_{mCYP3A4}$ and F_g values of 0.93 and 0.6, respectively were used and an AUCR value of 2.03 was determined indicating an approximately 2-fold increase in midazolam exposure when co-administered with voruciclib 50 mg once daily.

Therefore, during the period of coadministration with voruciclib, the dose of venetoclax was reduced by 50% to 200 mg once daily.

Effective half-life of voruciclib

In Study P1446A-05/19/08 and Study P1446A-05/20/08, voruciclib PK samples were collected for 24 hours post-dose after single and multiple administrations. Sample collection only during the 24-hour dosing interval precluded reliable estimation of terminal phase half-life. However, effective half-life may be calculated based on accumulation ratio (multiple dose $AUC_{(0-24)}$ divided by single dose $AUC_{(0-24)}$) using the following formula:

Accumulation Ratio = $1 / (1 - \exp(-k_{el} \times \tau))$.

Based on accumulation ratio, voruciclib effective half-life was estimated at the 600 mg and 350 mg dose levels in Study P1446A-05/19/08 and Study P1446A-05/20/08, respectively. These dose levels were chosen because of the large sample size of 16 and 24, respectively, thus permitting a robust estimation. Based on average accumulation ratios of 2.06 and 2.77, voruciclib effective half-life value was estimated to be 24 to 36 hours.

Preliminary PK results for voruciclib and venetoclax for Cohorts 12 (voruciclib 50 mg QOD) to 15 (voruciclib 150 mg QD) indicate that administration of multiple doses of voruciclib does not have an effect on venetoclax PK. In these cohorts, on Cycle 1 Day 21 (i.e., 7 days after the last voruciclib dose on Cycle 1 Day 14), plasma voruciclib concentrations were either below the lower limit of quantitation or very low. At the highest voruciclib dose level evaluated for PK (150 mg QD, Cohort 15), average plasma voruciclib concentration on Cycle 1 Day 21 was 8 ng/mL (less than 2% of maximum plasma concentration) indicating nearly complete elimination of voruciclib from the systemic circulation one week after the last dose. Lack of pharmacokinetic interaction at steady-state and very low voruciclib concentrations observed one week after the end of treatment justifies administration of the labeled dose of venetoclax on voruciclib treatment-free days. Therefore, in Cohorts 21–25 (voruciclib $IS_{3w,1w}$) the labeled dose of venetoclax (400 mg QD) may be administered on Days 22 to 28 of each cycle when voruciclib is not administered.

Sequence of administration

Per the [Venclexta \[US Prescribing Information\] Rev 2022](#), it is noted that P-gp substrates (such as voruciclib) should be administered at least 6 hours before venetoclax administration. However, this timing and sequence presents logistical considerations related to the collection of serial blood samples for PK analysis over the course of a treatment/PK sampling day. As venetoclax requires administration with food, it is administered first followed by voruciclib at least 2 hours after the meal, allowing for PK sampling through 8 hours post the venetoclax dose and pre-dose sampling on the subsequent day to be completed in the morning (see [Section 9.14.2](#)).

4.4. Dose-Limiting Toxicity (DLT)

A DLT will be defined as any of the following treatment-emergent adverse events (TEAEs) occurring in Cycle 1 of voruciclib monotherapy or voruciclib + venetoclax combination therapy that are clearly unrelated to the underlying disease or extraneous causes:

- Symptomatic nonhematological Grade ≥ 3 laboratory abnormalities or asymptomatic nonhematological Grade ≥ 3 laboratory abnormalities that fail to improve to Grade ≤ 2 within 72 hours
- Grade 3 vomiting lasting >48 hours despite recommended antiemetic support or any occurrence of Grade ≥ 4 vomiting
- Grade 3 diarrhea lasting >48 hours despite recommended antidiarrheal support or any occurrence of Grade ≥ 4 diarrhea
- All other Grade ≥ 3 nonhematological adverse event (AE) not listed above
- Grade 3 or higher TLS regardless of prophylaxis
- Hy's law cases
- Febrile neutropenia of any duration (not applicable to AML subjects)
- Grade 4 neutropenia lasting ≥ 7 days; or lasting ≥ 42 days and not due to progressive disease in AML subjects
- Grade ≥ 3 thrombocytopenia with Grade ≥ 2 bleeding or Grade 4 thrombocytopenia of any duration (not applicable to AML subjects)
- Grade 4 thrombocytopenia lasting ≥ 42 days (AML subjects only)
- Grade 4 anemia unexplained by underlying disease

Hy's law cases of drug-related hepatocellular injury are defined as elevated ALT or AST $\geq 3 \times$ ULN, elevated total bilirubin $>2 \times$ ULN without findings of cholestasis, and no other reason can be found to explain the combination of increased aminotransferase and serum total bilirubin, such as viral hepatitis, alcohol abuse, ischemia, pre-existing liver disease, or another drug capable of causing the observed injury.

Additionally, discontinuation of study drug in Cycle 1 due to an AE that is clearly unrelated to the underlying disease, or an extraneous cause will be considered a DLT.

Safety will be assessed by AEs graded according to National Cancer Institute Common Terminology Criteria for Adverse Events (NCI CTCAE) v5.0; laboratory safety tests including hematology (complete blood count [CBC]), serum chemistry; physical examination; vital signs; ECOG performance status; and 12-lead electrocardiogram (ECG).

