For subjects in the combination voruciclib + venetoclax cohorts, venetoclax is to be taken first (with a meal) followed by voruciclib taken at least 2 hours later (e.g., meal completed at 8 a.m. with venetoclax, dose voruciclib after 10:00 a.m.), with the exception of C2D1 when voruciclib is to be dosed 6 hours after venetoclax administration, after completion of the 6-hour PK sample collection.

Voruciclib tablets must not be chewed, crushed, or broken.

Dose Modifications

For subjects enrolled on voruciclib monotherapy cohorts, criteria for interrupting study drug treatment and requirements for re-treatment or discontinuation of study drug are provided in [Table 10](#) of the protocol.

For subjects enrolled on voruciclib + venetoclax combination cohorts, dose modifications for toxicities attributed to venetoclax or for the combined effect of voruciclib and venetoclax will be based on the [Venclexta US Prescribing Information](#) and are provided in protocol [Table 11](#).

Duration of Therapy

Subjects may continue to receive voruciclib monotherapy or voruciclib + venetoclax while there is evidence of clinical benefit (partial remission [PR] or better) in subjects with B-cell malignancies or AML by the end of Cycle 6 and acceptable toxicity as judged by the Investigator.

SAFETY PLAN**Dose-Limiting Toxicity (DLT)**

A DLT will be defined as any of the following treatment-emergent adverse events (TEAEs) occurring in Cycle 1 (first 28 days) of voruciclib monotherapy or voruciclib + venetoclax combination therapy that are clearly unrelated to the underlying disease or extraneous causes:

- Symptomatic nonhematological Grade ≥ 3 laboratory abnormalities or asymptomatic nonhematological Grade ≥ 3 laboratory abnormalities that fail to improve to Grade ≤ 2 within 72 hours
- Grade 3 vomiting lasting >48 hours despite recommended antiemetic support or any occurrence of Grade ≥ 4 vomiting
- Grade 3 diarrhea lasting >48 hours despite recommended antidiarrheal support or any occurrence of Grade ≥ 4 diarrhea
- All other Grade ≥ 3 nonhematological adverse event (AE) not listed above
- Grade 3 or higher tumor lysis syndrome (TLS) regardless of prophylaxis
- Hy's law cases
- Febrile neutropenia of any duration (not applicable to AML subjects)
- Grade 4 neutropenia lasting ≥ 7 days; or in AML subjects only lasting ≥ 42 days and not due to progressive disease

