Only the tablet formulation containing the voruciclib malonate salt will be used in the voruciclib plus venetoclax combination group.

Table 3: Dose Cohorts with Combination Voruciclib + Venetoclax (Amendment 11)

Cohort Dose Level	Doses and Schedule
12	voruciclib 50 mg QOD, administered IS _{2w,2w} + venetoclax administered QD × 28 days
13	voruciclib 50 mg QD, administered IS _{2w,2w} + venetoclax administered QD × 28 days
14	voruciclib 100 mg QD, administered IS _{2w,2w} + venetoclax administered QD × 28 days
15	voruciclib 150 mg QD, administered IS _{2w,2w} + venetoclax administered QD × 28 days
16	voruciclib 200 mg QD, administered IS _{2w,2w} + venetoclax administered QD × 28 days
17	voruciclib 250 mg QD, administered IS _{2w,2w} + venetoclax administered QD × 28 days
18	voruciclib 300 mg QD, administered IS _{2w,2w} + venetoclax administered QD × 28 days
19	voruciclib 350 mg QD, administered IS _{2w,2w} + venetoclax administered QD × 28 days

Abbreviation: QOD = once every other day

At the completion of the DLT period for each cohort, decisions to escalate in subsequent cohorts will be guided by SRC review of all available safety data, PK and PD data.

For Cohort 12, the dosing of voruciclib will be Days 3, 5, 7, 9, 11, and 13 of Cycle 1, and Days 1, 3, 5, 7, 9, 11, and 13 of Cycle 2 and beyond.

Dose escalation to the next cohort will be initiated after 3 subjects have completed 1 cycle with no reported DLTs, or after 6 subjects have completed 1 cycle with no more than 1 DLT (as defined in [Section 4.4](#)) and with the approval of the SRC after review of safety from the cohort under review.

Intra-patient dose escalation to the next dose in Cycle 2 or later cycle is allowed at the discretion of the investigator and after consultation with the Sponsor if the next dose level has been declared safe by the SRC. More specifically, a subject enrolled at a dose level X may have their dose escalated to the next dose level X + 1 after completing Cycle 1 without a DLT.

Dose escalation proceeds until assessment of clinical and PK parameters by the SRC establishes the safe BED for voruciclib in combination with venetoclax. More specifically, a voruciclib dose in combination with venetoclax that meets the following criteria:

- DLT not to exceed 1 in 6 patients, overall response rate (ORR) $\geq 30\%$, as compared to historical ORR of 19% with 400-800 mg venetoclax alone in relapsed/refractory AML ([Konopleva 2016](#)), and

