10.3.2. Analysis Populations

The Safety population is defined as subjects who receive at least one dose of study drug(s).

The DLT evaluable population includes subjects in dose escalation cohorts who complete the first cycle of treatment with at least 75% of study drug compliance or experience a DLT during the first cycle (28 days) of treatment.

The Efficacy evaluable population is defined as subjects who complete the first scheduled post-baseline efficacy evaluation (scheduled on C3D1 for B-cell lymphoma subjects and C2D1 for AML subjects) or develop progression of disease or death prior to the first scheduled post-baseline efficacy.

The PK population will include all subjects who receive at least 1 dose of voruciclib or venetoclax and have at least 1 non-missing post-dose concentration value.

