APPENDIX 3. SCHEDULE OF ASSESSMENTS - AML SUBJECTS ONLY – COMBINATION THERAPY

	Screening ^b	Cycle 1- Inclusive of Venetoclax Ramp-up ^c					Cycle 2		Cycle 3 and Subsequent Cycles ^d	End of Study ^e
	-28 to -1	1 ^a	2	3	8	14	1	14	1	30 days (± 3 days) Post Last Dose Study Drug
Informed consent	X									
Medical history/Prior Treatment/Demographics	X									
Physical examination	X	X								X
Symptom-directed exam ^f				X	X	X	X		X	
Vital signs ^g	X	X		X	X	X	X		X	X
Height	X									
Weight	X						X		X	X
ECOG performance status	X	X					X		X	X
Pregnancy test ^h	X	X					X		X	X
HIV testing ⁱ	X									
Hepatitis B and C testing ^j	X									
Adverse events ^k		X	X	X	X	X	X	X	X	X
Concomitant medication ^l	X	X	X	X	X	X	X	X	X	X
ECG ^m	X	X		X	X	X	X			X
CBC with differential ⁿ	X	X		X	X	X	X	X	X	X
Serum chemistry ^o	X	X	X	X	X	X	X	X	X	X
TLS risk assessment and monitoring ^o	X	X	X	X						
Coagulation ^p	X		X			X	X		X	X
Urinalysis (dipstick) ^q	X						X			X
Baseline chest x-ray ^r	X									
Issue and assess compliance diary ^s		X					X		X	
Dispense study drug(s) ^t		X					X		X	
Disease assessment, bone marrow aspirate ^u	X						X		X	X
Cytogenetics ^v	X									
Molecular mutations ^w	optional									
Blood for PD/biomarker assays ^x		X		X		X				
Blood for PK analysis	See specific PK collection timepoints in table below									

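### In AML, the Grade 4 neutropenia and thrombocytopenia DLTs require at least 42 days, but the DLT window and the escalation trigger rest on 28 days

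*Protocol*

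**What the plan says.** **The criteria.** Protocol Section 4.4 gives AML subjects their own duration conditions. Grade 4 neutropenia is a DLT if it meets the condition "or lasting ≥ 42 days and not due to progressive disease in AML subjects". The platelet criterion is "Grade 4 thrombocytopenia lasting ≥ 42 days (AML subjects only"), with no progressive-disease qualifier. All DLTs must also be treatment-emergent and clearly unrelated to the underlying disease or extraneous causes.

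**The window.** Section 4.4 begins "A DLT will be defined as any of the following treatment-emergent adverse events (TEAEs) occurring in Cycle 1". The synopsis is more specific: "occurring in Cycle 1 (first 28 days) of voruciclib monotherapy or voruciclib + venetoclax combination therapy". For combination cohorts the synopsis starts the DLT period at the first venetoclax dose. Section 10.3.2 admits to the DLT-evaluable population subjects who complete Cycle 1 with adequate compliance or who "experience a DLT during the first cycle (28 days) of treatment"; Section 10.3 repeats the 28 days. SAP 6.2 uses the first cycle as well.

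**The decision.** Section 4.1 and SAP 3.1.1 follow a cohort for 28 days. Section 4.3.2 states: "Dose escalation to the next cohort will be initiated after 3 subjects have completed 1 cycle with no reported DLTs", or after 6 subjects with no more than 1 DLT, subject to approval by the Study Review Committee (SRC). It also allows a subject's own dose to rise after a DLT-free Cycle 1.

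**What is absent.** No section extends the window to 42 days, delays the decision for an ongoing Grade 4 cytopenia, or says how an event confirmed later is credited to its cohort. The only other use of Day 42 is in Table 11 (Section 4.8.3), which governs dose modification and not escalation.

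**The concern.** Two listed DLT criteria have a duration longer than the period in which a DLT may occur. A subject with ongoing Grade 4 neutropenia or thrombocytopenia at Day 28 cannot yet have met either one, so that subject enters the 3 + 3 count as DLT-free. The same status feeds the mBED criterion of no more than 1 DLT in 6 and the permission for intra-subject escalation.

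This matters because Section 4.8.3 names myelosuppression as a potential overlapping toxicity of the two drugs, DLT incidence is part of the primary endpoint (Section 10.2), and escalation is continuing. The 300 mg cohort on the two-weeks-on schedule was enrolling when Amendment 12 was issued. That amendment also opens Cohorts 21–25, where Cycle 1 voruciclib runs over Days 3–21 instead of Days 3–14.

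**Working it through.** **Figure to reproduce.** The 28-day window is a definition, so there is nothing to derive. It is stated consistently in the synopsis, Sections 4.1, 10.3 and 10.3.2, and SAP 3.1.1. The design's target DLT rate of 20–25% (Section 10.3) cannot be recomputed, because the documents give no dose–toxicity curve.

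**Step 1: can a 42-day event fit in the window?** Counting the onset day as the first, the 42nd day falls on study day (onset + 41).

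| Onset day | 42nd day | Days past Day 28 | Event days observed by Day 28 |
|---|---|---|---|
| 1 | 42 | 14 | 28 |
| 8 | 49 | 21 | 21 |
| 15 | 56 | 28 | 14 |
| 22 | 63 | 35 | 7 |
| 28 | 69 | 41 | 1 |

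To finish by Day 28, onset would have to be on Day 28 − 41 = Day −13. That is before treatment, so the event would not be treatment-emergent. By contrast, the 7-day neutropenia criterion for B-cell subjects fits with onset as late as 28 − 6 = Day 22.

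**Step 2: the onset reading.** Suppose *occurring* means onset in Cycle 1, and the decision is taken when the last subject reaches Day 28. A subject enrolled s days before the last one is then on Day 28 + s. Confirmation in time needs 28 + s ≥ onset + 41, so s ≥ onset + 13.

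- Onset Day 1: at least 14 days ahead of the last subject.
- Onset Day 14: at least 27 days ahead.
- Onset Day 28: at least 41 days ahead.
- Last subject (s = 0): impossible for any onset on treatment.

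If a cohort is expanded to 6, the first 3 subjects have about 56 days of follow-up at the decision, enough for onset up to Day 56 − 41 = Day 15.

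**Step 3: effect on escalation (illustration only).** The documents give no cytopenia rates. Assume a per-subject rate v of DLTs visible by Day 28 and an independent rate h of qualifying 42-day cytopenia. The total rate is t = 1 − (1 − v)(1 − h). The 3 + 3 rule escalates with probability (1 − p)³ + 3p(1 − p)⁵, where p = v if these cytopenias are not counted and p = t if they are.

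| v | h | t | Not counted | Counted |
|---|---|---|---|---|
| 0.10 | 0.10 | 0.19 | 0.906 | 0.730 |
| 0.10 | 0.20 | 0.28 | 0.906 | 0.536 |
| 0.10 | 0.30 | 0.37 | 0.906 | 0.360 |
| 0.20 | 0.10 | 0.28 | 0.709 | 0.536 |
| 0.20 | 0.20 | 0.36 | 0.709 | 0.378 |

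The gap shrinks to nothing as h approaches 0.

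**Step 4: would the data exist?** In Appendix 3 the row "CBC with differential" is marked at Cycle 2 Day 1 and at Cycle 2 Day 14, which is study Day 28 + 14 = 42. A count is therefore planned on the first day a Day 1 event could qualify, but after the decision point.

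**The case against.** **The long duration may be deliberate.** Prolonged cytopenia is expected in AML, and Section 3.1 sets no minimum neutrophil or platelet count for AML subjects. That is a clinical choice and is not challenged here. It also means the rate of cytopenia attributable to treatment could be well below the rates illustrated. What stands is the mismatch between duration and window.

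**Onset may be what is meant.** Section 4.4 says only Cycle 1, without the 28 days. A late-confirmed event could then still be tabulated, since the subject is evaluable through completing Cycle 1 and SAP 8.7.1 sets no time limit. This is a fair reading, but the synopsis and Section 10.3.2 point the other way, and it does not help the last subject enrolled.

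**A reader might infer that myelosuppression cannot affect the MTD or mBED at all.** The documents do not support that. Grade 4 anaemia unexplained by underlying disease has no duration condition, and Cycle 1 discontinuation for an unrelated-to-disease adverse event is a DLT. The SRC reviews all available safety data and may hold enrolment (Sections 4.3.1.1 and 4.3.2, SAP 7.10). The MTD definition in Section 4.6 names no 28-day limit, SAP 3.1.2 bases the mBED on tolerability over two or more cycles, and expansion monitoring looks at cumulative toxicity (Section 4.5). These safeguards are real, but SRC review is discretionary and does not change a DLT count.

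**A reader might also infer that the report of no DLTs from 50 mg every other day to 250 mg daily missed such events.** That is not shown. If cohorts opened in the sequence the escalation rule requires, the earlier ones had further calendar time before Amendment 12. The documents do not say whether events confirmed after Day 28 were included.

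**Conclusion.** The inconsistency stands and should be resolved before further escalation decisions rely on it. Under the synopsis wording, the AML neutropenia and thrombocytopenia DLTs cannot be met: the shortfall is at least 14 days, and this needs no assumption beyond the documents' own definitions. Under an onset reading the criteria can work for some early-enrolled subjects or in a cohort expanded to 6, but never for the last subject at the decision.

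The conclusion is limited to these two criteria. It does not extend to all haematologic toxicity, and it does not show that any past cohort was wrongly cleared. The effect on escalation is unknown. The probabilities above rest on assumed, independent rates and serve only to show a range.

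**What to change.** Reconcile the duration criterion with the window in the synopsis, Protocol Sections 4.1, 4.3.2, 4.4, 4.12 and 10.3.2, and SAP 6.2, with matching text in Section 10.3 and SAP 3.1.1. The thresholds and their qualifiers remain the sponsor's decision. The text should state:

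1. Whether *occurring* in Cycle 1 means onset or completion.
2. How to count a subject whose Grade 4 event meets every other Section 4.4 condition (treatment-emergent, clearly unrelated to the disease or extraneous causes and, for neutropenia only, not due to progressive disease) but is unresolved at the end of Cycle 1. One option is to treat the subject as not yet evaluable until the event resolves or reaches the stated duration.
3. Whether the no-DLT summary for the earlier combination cohorts in Section 4.3.2 included events confirmed after Day 28.

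The cost is wording, plus a possible delay to a cohort decision of about 2 weeks for Day 1 onset (14 days) and up to about 6 weeks for onset at the end of Cycle 1 (41 days). How often this would occur cannot be judged from the documents.

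A separate, minor point: Appendix 3 schedules no blood count between Cycle 1 Day 14 and Cycle 2 Day 1. One could be drawn at the Day 21 visit already required for PK (Tables 14 to 17).
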